8.3 Subject Disposition

Subject disposition including the number of subjects enrolled and number of subjects completing the study (and completing each study visit) will be tabulated. The percentage of subjects completing the study will be based on the total number enrolled.

Protocol deviations will also be summarized. Subject withdrawals and the reasons for withdrawal will also be summarized.

All data collected on the withdrawn subjects prior to withdrawal will be included in all analyses. However, if a protocol deviation is reported for a withdrawn subject, the subject may be excluded from the Per Protocol analysis set if the deviation is determined to potentially affect study outcomes.

8.4 Demographic and Other Baseline Characteristics and Concomitant Medications

Demographic data, medical history and concomitant medications will be summarized by means of descriptive statistics based upon the ITT dataset.

8.5 Control of Systematic Bias

Several measures are incorporated into the study design to help minimize bias as follows:

- This is a multi-center trial to help ensure that investigator or site or subject enrollment bias is minimized. Investigational sites are limited to enrolling no more than 18 subjects.
- Consecutively eligible subjects should be enrolled into the study to minimize selection bias.
- A Medical Monitor will review all assessments of seriousness and relatedness for adverse events, and the Medical Monitor's determinations will supersede the site-reported assessments in summaries of the data.

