The Medical Monitor (an independent physician not participating as a clinical investigator in the clinical study) will review and assess in conjunction with the Sponsor all AEs considered by the investigator to be at least possibly related to the use of the ASSURE WCD System to determine if they are reportable to the FDA as Unanticipated Adverse Device Effects (UADEs) per the definition in Section 11. The Medical Monitor will also review all Serious Adverse Events considered by the investigator to be at least possibly related to the use of the ASSURE WCD System to the ASSURE WCD System to verify relatedness and the Serious classification.

Endpoint Review Committee

An independent panel of board-certified electrophysiologists (physicians not participating as clinical investigators in the clinical study) will review all episodes recorded by the ASSURE WCD and/or the subject's ICD in accordance with the *Endpoint Review Committee (ERC) Charter for ASSURE WCD Clinical Evaluation - Detection and Safety Study (ACE-DETECT)* (3334131). These annotations will then be used in the statistical analysis to classify the episodes to calculate the study outcome measures.

Replacements

Subjects who are withdrawn from the study will not be replaced.

Sponsor or Regulatory Agency Termination of the Study

Although the Sponsor intends to complete the study, the right is reserved to discontinue the study at any time for clinical or administrative reasons, or if required by the local regulatory authority.

End of Study

The end of study will be defined as the date of the last visit of the last subject. A summary of the End of Study report will be sent to relevant regulatory authorities and Institutional Review Boards (IRBs) within 6 months of the end of the study.

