- Fit Garment to subject in accordance with the sizing chart and instructions provided in the System Training Manual. *Subjects with an under bust chest circumference greater than 52 inches or less than 28 inches are not eligible to be enrolled.*
- Photograph Garment fit (torso only, not subject's head) from both lateral views, the anterior view and the posterior view.
- Set up the WCD including subject ID entry, and synchronization of the WCD internal clock to the current time and time zone. VT/VF detection parameters will remain at default settings. (Refer to the System Training Manual).
- Register the study subject on the CareStation remote monitoring website (Add New Patient) using their study subject ID number.
- Verify Garment fit per System Training Manual using the tablet. Save tablet screen images of the Patient Management, Device Status and WCD Settings screens including the ECG signals.
- Schedule subject to return for follow up (Visit 2)
- Notify the subject that they will receive phone calls on Days 7 +/- 2, 14 +/-2, 21+/- 2, and 28 +/- 2 during which they can ask questions, and during which they will be asked about usage (how long they have been wearing the system), and if they experienced any discomfort or injury. Schedule these weekly phone calls with the subject.

Weekly Phone Calls to Study Subject

On each of Day 7 +/- 2, Day 14 +/- 2, Day 21 +/- 2, and Day 28 +/- 2 the site RC will call the study subject. In preparation for the call, the RC will review daily usage using the CareStation website and will record the usage data in the CRF.

• Record subject questions and responses in the CRF, noting any questions that require additional follow up and when the subject was called again with the answer(s).

Kestra Medical Technologies, Inc. Protocol 3324582_B

- Record subject's explanation for any usage less than 22 hours per day³ since the previous call.
- Ask the subject if they have experienced any discomfort or injury during the previous week. If yes, and the investigator determines that the symptoms are at least possibly related to use of the system, record as an AE in the CRF and gather supporting documentation as appropriate, e.g. description, photograph.

Visit 2: Study Exit Visit

At Visit 2 the following will be performed:

- Photograph garment fit (torso only) from both lateral views, the anterior view and the posterior view.
- Remove the Garment.
- Record WCD System Return (all components).

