11 STUDY ASSESSMENTS

This section describes the study assessments. For timing of study assessments, see the Schedule of Events (Appendix A).

Demographic Data

Demographic data, such as age, sex, race, and ethnicity will be collected on the CRF

Abbreviated Medical History

An abbreviated medical history as specified in the CRF, including but not limited to cardiac diagnosis and skin allergies will be obtained for each subject at screening and updated any time the Investigator learns of information that might affect the subject's eligibility to continue participation in the study or to identify AEs.

ICD Interrogation and Report Generation

ICD Interrogation at Visit 1 (collect Baseline ICD Documentation via direct interrogation) and at Visit 2 (Obtain ICD summary report via the ICD remote management system or direct interrogation) must be done by qualified site personnel.

BORG Comfort Scale

Subjects will be asked by the research coordinator at baseline and again at the follow up visit to locate and grade the severity of any discomfort they experience on their upper body. This will be recorded on a BORG comfort scale/map as specified in CRFs.

Wearability Assessment

A Wearability Assessment (as specified in the CRF), including a review of skin abnormalities on the upper body and/or musculoskeletal conditions, and measurement of height and weight, will be performed by study personnel. Abnormal findings at Visit 1 will be used to reassess eligibility. If the subject is enrolled, then the findings will be recorded in the CRFs as baseline conditions. The Wearability Assessment will also be performed at Visit 2 after the System has been removed. Height will not be measured or recorded at Visit 2. Abnormal findings that were not present at baseline or have worsened from baseline and are determined by the investigator to be at least possibly related to use of the WCD will be recorded in the CRFs as AEs.

Concomitant Medical Devices and Equipment

Use of allowed concomitant medical devices and durable medical equipment will be recorded in the CRFs (e.g. CPAP, walker, wheelchair).

Clinical Laboratory Tests

Pregnancy testing by urinalysis will be performed for women of child bearing potential to verify eligibility prior to enrollment. Test sticks will be provided by the Sponsor.

Evaluation of Adverse Events

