Adverse events (AEs) as defined below will be monitored continuously during the study from the time the subject is considered enrolled through resolution. Subjects will be instructed to report all AEs during the study, and study personnel will interview the subjects regarding new AEs during each weekly phone call follow up. AEs may be reported by the subject, discovered by Investigator questioning, or detected through physical examination or other means at the study exit visit.

Device Usability Survey

A device Usability Survey will be administered at Visit 2.

Definitions

For the purposes of this study, an **AE** is defined as any untoward medical occurrence in a subject during the study that in the opinion of the investigator is at least possibly-related to use of the ASSURE WCD System.

A serious adverse event (SAE) is defined as any adverse event that:

- Leads to death
- Leads to serious deterioration in the health of a subject that:
 - Results in a life-threatening illness or injury, or
 - Results in a permanent impairment of a body structure or a body function, or
 - Requires in inpatient or prolonged hospitalization \geq 24 hours, or
 - Results in medical or surgical intervention to prevent life-threatening illness or injury or permanent impairment to a body structure or function, or
 - Leads to fetal distress, fetal death or a congenital anomaly or birth defect.

Adverse Device Effect (ADE) is an adverse event related to the use of an investigational medical device.

Anticipated Adverse Device Effects (AADE) are those events related to the use of the device that are reasonably expected to occur as a result of the subject's participation in

the study. The following are AADEs based on results from the series of previous feasibility studies listed in Section 6 and the system engineering hazard analysis:

- Mild to moderate skin irritation
- Muscle Strain
- Emotional discomfort e.g. anxiety, uncomfortable or claustrophobic feelings
- Fall Injury
- Bruising
- Pinched Fingers
- Shoulder discomfort
- Skin Infection (bacterial or yeast)
- ICD System Infection

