An **Unanticipated Adverse Device Effect (UADE)** is any serious adverse effect on health or safety or any life-threatening problem or death caused by, or associated with the device, if that effect, problem, or death was not previously identified in nature, severity, or degree of incidence in this protocol; or any other unanticipated serious problem associated with the device that relates to the rights, safety, or welfare of subjects.

All AEs will be assessed by the investigator according to:

- Whether the event is serious (SAE);
- The severity of the event (mild, moderate, severe); and
- The relationship of the event to device use (possibly, probably, or definitely related)
 - Possibly Related There is a reasonable possibility that the AE may have been primarily caused by device use. The AE has a reasonable temporal relationship to the use of the device and follows a known or expected response pattern to device, but alternative etiology is equally or more likely compared to the potential relationship to the use of the device.
 - Probably Related There is a reasonable probability that the AE may have been primarily caused by device use. The AE has a reasonable temporal relationship to the use of the device and follows a known or expected response pattern to device. Note: this definition assumes no

alternative etiology is equally or more likely compared to the potential relationship to the use of the device.

 Definitely Related – The AE has a strong causal relationship to device use. The AE follows a strong temporal relationship to the use of the device, follows a known response pattern to the device, and cannot be reasonably explained by known characteristics of the subject's clinical state or other therapies.

Whenever possible, the Investigator should group signs or symptoms that constitute a single diagnosis under a single AE term (e.g. redness and swelling can be combined under skin irritation).

Baseline conditions e.g. mild eczema, and AEs identified at Visit 1 following enrollment will be documented during the Wearability Assessment. Baseline conditions are not considered adverse events unless the condition worsens because of study device use.

Adverse Event Reporting Procedures

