An estimate of the inappropriate shock rate will be calculated as the product of the WCD False Positive Alarm Rate (the Primary Outcome measure of this study) and the Missed Shock Alarm Rate. The Missed Shock Alarm Rate was derived from two prior studies during which high priority alarms (shock alarms) were delivered randomly to study subjects. A "Missed Shock Alarm" was one during which the subject failed to respond to the shock alarm within 20 seconds following alarm activation. Data was obtained both during sleep (GDR 3333597 ASSURE UISim Sleep Study) and during normal daily activities (GDR 3334121 ASSURE UISim 7-day study).

Adverse Events

AEs will be summarized using the SAF subject set. Separate summaries of AEs at least possibly related to device use and by severity (as reported by the Investigator and reviewed by the Medical Monitor) will be prepared. UADEs will also be summarized. AEs leading to withdrawal from the study will be listed and tabulated.

Subgroup Analysis

Subgroup analyses are exploratory and will be specified in the Statistical Analysis Plan.

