4.5 Adverse Events

All adverse events reported over the course of the study will be summarized and tabulated by category, seriousness, and relationship to the study device (possibly, probably or definitely). No formal statistical testing is planned.

5. Analysis Methods

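### The Medical Monitor's overriding review cannot add a device-related event that the investigator did not record, so it does not control under-attribution

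*SAP*

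**What the plan says.** **Entry to the safety data.** Protocol 11 (Definitions), repeated in SAP 6.1, makes an untoward occurrence an AE only if it "in the opinion of the investigator is at least possibly-related to use of the ASSURE WCD System". A serious AE (SAE) is an AE that meets a seriousness criterion, so it inherits this condition. The recording rules follow suit. On the weekly calls in Protocol 10, sites act if the "investigator determines that the symptoms are at least possibly related to use of the system, record as an AE in the CRF". At exit, under the Wearability Assessment in Protocol 11, it is findings that are new or worse and are "determined by the investigator to be at least possibly related to use of the WCD will be recorded in the CRFs as AEs".

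**What the Monitor receives.** Under Protocol 9 the Monitor "will review and assess in conjunction with the Sponsor all AEs considered by the investigator to be at least possibly related" to the device, in order to decide whether they are reportable as UADEs. A separate sentence has the Monitor check relatedness and seriousness for SAEs, again only those that the investigator calls related.

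**What the Monitor's view does.** SAP 6.1 uses the Monitor's view of seriousness and relatedness in place of the investigator's. SAP 8.5 says that the Monitor's "determinations will supersede the site-reported assessments in summaries of the data" and lists this among the measures that reduce bias. Protocol 12 describes the AE summaries "as reported by the Investigator and reviewed by the Medical Monitor" and states no override.

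**How events are tabulated.** SAP 4.5 has AEs "summarized and tabulated by category, seriousness, and relationship to the study device (possibly, probably or definitely", and the list of levels ends there. Protocol 11 uses the same three levels.

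**The concern.** In a single-arm, open-label device study, the attribution error that matters most for safety is an event wrongly called unrelated. Subjects here have LVEF ≤ 40% and an ICD, so hospitalizations and deaths with plausible causes other than the device can be expected. The anticipated device effects in Protocol 11 include fall injury, skin infection and ICD system infection, each of which could also be put down to something else. Protocol 9 itself foresees short hospital stays for complications unrelated to the study, and nothing has the Monitor check that judgement.

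An independent review that overrides the site would be a sensible safeguard if it saw both sides of the attribution decision. Here it comes after that decision and sees one side only. At stake is the count of device-related AEs, a secondary endpoint in Protocol 8 and SAP 4.3, in a study meant to support a premarket approval application.

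**Working it through.** No sample size, power or error rate is involved, so the check follows an event from occurrence to table.

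**Step 1: the bound.** Let I be the set of events that the investigator judges at least possibly related, and M the set that the Monitor judges related. By the AE definition and the recording rules, only events in I are recorded as AEs. By Protocol 9, the Monitor is sent only events in I. Hence M lies within I, and the Monitor-based number of related events is at most the investigator's number. An event outside I is neither an AE nor an SAE, and no section routes it to the Monitor.

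**Step 2: which changes the text allows.**

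| Change to the site's assessment | Open to the Monitor? | Basis |
|---|---|---|
| Judged unrelated by the investigator → related | No | AE definition; Protocol 9 |
| Related → not related | Implied, but no level or table row exists for it | SAP 6.1 and 8.5; scale in Protocol 11 and SAP 4.5 |
| Possibly → probably or definitely related | Yes, for events within scope | SAP 6.1 and 8.5 |
| Non-serious → serious | Yes on the SAP 8.5 wording; not on Protocol 9 or SAP 6.1, which start from SAEs | as listed |
| Recorded AE → UADE | Yes | Protocol 9; SAP 6.1 |

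Only the first row concerns under-attribution, and it is closed.

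**Step 3: the Monitor's scope in the four places that state it.**

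- Protocol 9: all recorded AEs for UADE reportability; relatedness and seriousness for SAEs only.
- SAP 6.1: the same split, followed by an override for safety data without that limit. For a non-serious AE there may be no Monitor assessment of relatedness to use.
- SAP 8.5: seriousness and relatedness for all AEs, with override.
- Protocol 12: investigator report with Monitor review, and no override.

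These cannot all be followed. For a non-serious AE, whether the Monitor's relatedness is even assessed depends on which section the analyst reads.

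**The case against.** A reader might infer two stronger conclusions, and the documents support neither.

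The first is that the review can work only in the device's favour. It cannot be put that way. The Monitor may raise the degree of relatedness, which is itself tabulated, may raise seriousness on the SAP 8.5 wording, and may designate a UADE. The one-sidedness is confined to the related/unrelated decision. The sponsor's part in the AE review in Protocol 9 belongs to the UADE determination; the sentence on verifying SAE relatedness does not mention it.

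The second is that an AE downgraded by the Monitor disappears from the results. No rule says so. AE status rests on the investigator's opinion, AEs are also tabulated by type and severity, and SAP 6.1 provides a listing of all of them. What is missing is a rule and a row for an AE that the Monitor finds unrelated.

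Three further points carry weight:

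- Events called unrelated leave traces. Deaths are dated withdrawals and are summarized (Protocol 9, SAP 6.1), daily use below 22 hours must be explained (Protocol 10), and long gaps in wear are investigated (SAP 8.1). None of these routes leads to an independent judgement of relatedness.
- The threshold is permissive: *possibly related* applies even when another cause is equally or more likely. That makes under-attribution less likely but does not make it correctable. All three levels also call for a known or expected response pattern, which a novel effect might not meet.
- Collecting only device-related events matches the endpoint, the device has shocks and shock alarms disabled, and the secondary endpoints are exploratory without performance criteria. So no success decision depends on this count. This limits the importance of the point but does not make the SAP 8.5 statement correct.

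**Conclusion.** The point stands in limited form. As written, the Monitor's override cannot correct an event that the investigator wrongly judged unrelated, so SAP 8.5 claims more protection than the design gives. The Monitor's scope is also inconsistent between Protocol 9, Protocol 12, SAP 6.1 and SAP 8.5.

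The size is structural: no upward correction to the number of related events is possible, whatever the true rate of misattribution. The documents give no basis for estimating how many events are affected. The 30-day pilot in Protocol 6 (8 AEs in 6 of 32 subjects) does not help, because its subjects came from the general population and its events were minor skin irritation and garment scratches. Any assumed rate of downgrading would be invention.

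The conclusion assumes that sites follow the AE definition and that the Monitor works from what Protocol 9 sends. A separate Monitor procedure outside these documents could change it. It does not touch the primary endpoint.

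**What to change.** 1. **Protocol 11, with the matching sentence in Protocol 9.** Have sites record every death and inpatient hospitalization during the wear period regardless of attribution, and send these to the existing Medical Monitor for relatedness. Add a *not related* level to the scale so that the existing AE form can hold them. The secondary endpoint can stay limited to events that are at least possibly related.
2. **SAP 6.1 and 8.5, and the table in SAP 4.5.** Tabulate investigator and Monitor relatedness side by side, with a *not related* row, so that the treatment of a downgraded AE is explicit.
3. **Protocol 9, Protocol 12, SAP 6.1 and SAP 8.5.** State one scope for the Monitor (all AEs or SAEs only) and one rule on whose assessment is summarized.

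If item 1 is not adopted, SAP 8.5 should not claim bias control for under-attributed events.

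**Cost.** Items 2 and 3 are mainly wording and one extra column; item 3 also touches the protocol. Item 1 needs an IRB-approved amendment and a small form change. The number of extra forms is unknown. Purely as an illustration, if 1% to 5% of 130 subjects had such an event in 30 days, that is 130 × 0.01 = 1.3 to 130 × 0.05 = 6.5 forms. Weekly calls and the questions about low usage mean that sites would often learn of these events anyway. The related-event count may come out slightly less favourable.

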8.6 Pooling Data Across Centers

Approximately ten (10) investigational sites in the US will be participating in this study. The analyses will be presented using data pooled across study centers. Comparability between study sites may be examined using summary statistics calculated by site. A formal assessment of poolability of subjects across investigational sites is not planned.

9. Changes to Planned Analyses

Any changes to the planned statistical analyses made prior to analysis of the primary endpoint will be documented in an amended SAP approved prior to performing said analysis. Any unanticipated changes from the planned statistical methods after analyzing the primary endpoint data will be documented in the clinical study report along with the reason for deviation.

10. Definitions

Alarm Definitions (for the Primary Endpoint)

When initial arrhythmia detection criteria are met, the ASSURE WCD opens an Episode and begins storage of ECG signals. If the rhythm is sustained for the confirmation period, a Shock Alarm Event Marker is recorded. Each Shock Alarm Event Marker will be reviewed and annotated per the definitions and instructions in the *Endpoint Review Committee (ERC) Charter for ASSURE WCD Clinical Evaluation - Detection and Safety Study (ACE-DETECT)* (3334131). Each Shock Alarm Event Marker will be classified for the primary endpoint as follows:

- **True Positive Alarm**: The presence of a WCD Shock Alarm Event Marker within a recorded Episode where the Shock Alarm has been annotated as:
 - Rhythm Type VT/VF with HR ≥ 153 bpm (170 bpm 10%)
- **False Positive Alarm**: The presence of a WCD Shock Alarm Event Marker within a recorded Episode where the Shock Alarm has been annotated as:
 - Rhythm Type **Other**OR
 - Rhythm Type Uncertain (presumed non-shockable)
 OR
 - Rhythm Type VT/VF with HR < 153 bpm (170 bpm 10%)

Episode Detection (for the secondary Endpoint)

All WCD Episodes, and ICD Episodes for which there is not a corresponding WCD Episode, will be reviewed and annotated per the definitions and instructions in the *Endpoint Review Committee (ERC)* Charter for ASSURE WCD Clinical Evaluation - Detection and Safety Study (ACE-DETECT) (3334131). These annotation results will be used to classify the detections according to the following definitions:

- True Positive Detection: A WCD recorded Episode (with or without a Shock Alarm Event Marker) annotated as Rhythm Type VT/VF with HR ≥ 153 bpm (170 - 10%)
- Missed Event (False Negative Detection): An Episode recorded by the ICD but not by the WCD when it is confirmed that the WCD was being worn, and where the ICD Episode is annotated as Rhythm Type VT/VF with HR ≥ 187 bpm (170 + 10%) and Duration ≥ 20 seconds.

11. Revision History

Revision	Description of Changes	Revision Date
1	Initial description of analyses	19 MAR 2019

DOCUMENT NUMBER: DHF-00577-01

TITLE: ACE-DETECT Study Statistical Analysis

REV A

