2.1 Study Design/Overview

The ASSURE WCD Clinical Evaluation – Detection and Safety Study (ACE-DETECT) is a multicenter single arm open label evaluation. All subjects will be fitted with the WCD and will be trained and provided written instructions for use, including safety precautions and adverse event reporting. Demographic data and limited medical history data will be collected. The subjects will be asked to complete a BORG Comfort Scale at Visit 1 (baseline). Subjects will wear the device for approximately 30 days during normal daily activities including sleep. Research Coordinators will conduct weekly phone interviews with the subjects during the participation period to address subject questions, review potential adverse events, and review usage. Subjects will return for a final visit, Visit 2, at the end of the wear period. At Visit 2 subjects will be interviewed regarding any adverse events they may have experienced since the most recent phone follow-up and the status of any adverse events that were recorded during the participation period. They will also be asked to complete a device usability survey and the BORG Comfort Scale after the device is removed. All episodes recorded by the ASSURE WCD, the subject's ICD, or other devices when available, will be reviewed by independent clinical experts.

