4.4 Subgroup Analyses

Subgroup analyses based on, but not limited to, gender, age, BMI and baseline QRS width will be provided on the primary effectiveness endpoint. These analyses will be regarded as exploratory, and have been selected for the following reasons:

- Gender The ASSURE WCD is available in two styles (male and female). Garment fit may influence false alarm performance.
- Age Higher levels of activity may be associated with higher levels of noise, and activity levels
 may be influenced by age. Subgroups will be based on a cutoff point of 75 years (<75/≥75).
- BMI Data presented previously on the LifeVest suggest that obese subjects experience a significantly higher percentage of noise, which may influence false alarm performance. (Wan C et al. ESC 2013. The impact of body mass index on wearable cardioverter defibrillator efficacy. Abstract P4926 Poster.) Subgroups will be based on a cutoff point of 30 (</≥ 30).
- QRS width Variable used for rhythm classification in the ASSURE WCD detection algorithm.
 Subgroups will be based on a cutoff of 120 ms (</≥ 120).
- ICD Device Type Subjects are eligible for enrollment with either a single or dual chamber ICD. Identification of Episode Rhythm type may be facilitated by the presence of a dual chamber ICD.

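### An ICD-recorded VT/VF paired with a WCD Episode that is not annotated as VT/VF at 153 bpm or more counts as neither a True Positive Detection nor a Missed Event, and its ICD record need not be annotated

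*SAP*

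**What the plan says.** The scope of review is stated in two ways.

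- **Broad.** SAP 2.1: "All episodes recorded by the ASSURE WCD, the subject's ICD, or other devices when available, will be reviewed by independent clinical experts". Protocol Section 9, Endpoint Review Committee, says that the panel "will review all episodes recorded by the ASSURE WCD and/or the subject's ICD in accordance with the" committee's charter. The Study Procedures row of Protocol Section 3 agrees.
- **Narrow.** SAP Section 10, Episode Detection, and the same paragraph in Protocol Section 12: "All WCD Episodes, and ICD Episodes for which there is not a corresponding WCD Episode, will be reviewed and annotated". Neither document defines what makes two Episodes correspond.

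The secondary classes are the same in both documents.

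- A True Positive Detection is "A WCD recorded Episode (with or without a Shock Alarm Event Marker) annotated as Rhythm Type VT/VF with HR ≥ 153 bpm".
- A Missed Event is "An Episode recorded by the ICD but not by the WCD when it is confirmed that the WCD was being worn", where the ICD Episode is annotated as VT/VF of at least 187 bpm lasting at least 20 seconds.

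Appendix A of the SAP gives a listing with WCD and ICD columns side by side, including a yes/no field for ICD VT/VF above 187 bpm for more than 20 seconds. It assigns no class to a row in which the two sides disagree.

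**The concern.** The two classes do not cover every pairing of WCD and ICD records. As soon as the WCD opens an Episode, a Missed Event is ruled out, whatever that Episode is later judged to show. If the committee does not annotate it as VT/VF at 153 bpm or more, it is not a True Positive Detection either. The narrow scope rule then removes the requirement to annotate the ICD record that could settle the question.

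This is a foreseeable case. The protocol names ECG noise as the reported main cause of false alarms with the comparator device, and Uncertain is a planned annotation. The ICD data are collected to find events that the WCD missed (Protocol Section 10, Visit 1), and stored electrograms are gathered for all new ICD episodes at Visit 2. SAP 4.2 also raises enrolment from about 105 to at least 130 subjects to improve the chance of seeing a true ventricular event. With so few events expected, a class left undefined until the data are in would have to be settled after the fact, on the very events that this endpoint is meant to describe.

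**Working it through.** **1. The plan's own event count.** Inputs: 24 shockable events per 100 patient-years (Protocol Section 12, secondary endpoints); at least 130 subjects and 14 hours of wear a day (SAP 4.2); about 30 days of wear (SAP 2.1); and 22 hours a day, the usage level below which Protocol Section 10 asks for an explanation.

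Expected events = 0.24 × subjects × 30 / 365.25 × (wear hours / 24).

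- Continuous wear: 130 × 30 / 365.25 = 10.68 patient-years; × 0.24 = 2.56 events.
- 22 hours a day: 2.56 × 22/24 = 2.35 events.
- 14 hours a day: 2.56 × 14/24 = 1.49 events.

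The protocol's figure of about two is reproduced.

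**2. The definitions applied to each pairing.** Take an ICD Episode during confirmed WCD wear that would meet the rhythm, rate and duration limits for a Missed Event.

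| WCD record | True Positive Detection? | Missed Event? | ICD annotation required by Protocol 12 / SAP 10? |
|---|---|---|---|
| Episode annotated VT/VF, HR ≥ 153 bpm | Yes | No | No |
| No Episode | No | Yes | Yes |
| Episode annotated Other | No | No | No |
| Episode annotated Uncertain | No | No | No |
| Episode annotated VT/VF, HR < 153 bpm | No | No | No |

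The last three rows have no class. The event is best called ICD-recorded rather than ICD-proven, because the stated rule does not require anyone to annotate that ICD Episode.

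**3. Link to the alarm definitions.** If the WCD Episode in one of the last three rows carries a Shock Alarm Event Marker that is annotated the same way, the marker is a False Positive Alarm for the primary endpoint. The gap is therefore in the secondary classes only. The alarm classes do cover these annotations.

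**4. Scale.** One unclassified pair would be set against an expected total of 1.5 to 2.6 events. The 24 per 100 patient-years is built from appropriate-shock and non-sustained VT rates and is not limited to 187 bpm for 20 seconds. It therefore does not count exactly the events at issue, and those are probably fewer. Nothing in the documents gives the chance that a pair disagrees.

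**The case against.** The strongest reply is that the annotation rules are delegated to the Endpoint Review Committee Charter (3334131), which is not among the documents. It may tell readers to look at the paired ICD electrogram. SAP 4.4 hints at this: "Identification of Episode Rhythm type may be facilitated by the presence of a dual chamber ICD". This stands to the extent that one cannot say the paired ICD record is never read, only that Protocol Section 12 and SAP Section 10 do not require its annotation. Charter practice could make disagreement rarer, but it would not add the missing class to the stated definitions.

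It is also fair to say that nothing vanishes from the report. The secondary output is summarised episode by episode, and the Appendix A row would show both sides. What is missing is the class and a required ICD annotation, not the data. The endpoints are exploratory with no performance criteria (SAP 5.2), so the consequence is limited to descriptive reporting.

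Three stronger readings are tempting, and the documents do not support them.

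- *That alarm classification for the primary endpoint ignores ICD data.* The restriction on ICD Episodes stands under the secondary-endpoint heading. The alarm paragraph contains no such bar, and Data Sources in Protocol Section 12 draws both endpoints from review of ICD and/or WCD Episodes.
- *That such a pair shows the device failing to recognise VT/VF.* Rhythm Type is the committee's reading. The WCD opens an Episode because its initial detection criteria were met, and that Episode may even carry a Shock Alarm Event Marker. The disagreement may lie in how readable the stored ECG was.
- *That the gap costs 39% to 67% of the events.* Those figures are only 1/2.56 and 1/1.49. They assume that one disagreement occurs and use a rate that includes non-sustained VT. They are not an effect size.

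**Conclusion.** The point holds for the secondary endpoint. The two statements of scope conflict in both documents. Under the narrower one, an ICD-recorded VT/VF of at least 187 bpm and at least 20 seconds, paired with a WCD Episode annotated Other, Uncertain or VT/VF below 153 bpm, falls outside both classes.

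The conclusion on the definitions rests on the printed text alone. Its practical size rests on the protocol's event rate and on wear time, and the frequency of disagreement is unknown. With about two events expected, a single pair would change how the summary reads. It would not change the primary hypothesis test, the sample size or the significance level. The correction is worth making before the data are read because it is cheap and avoids an after-the-fact decision on a very small number of events.

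**What to change.** 1. Reword Episode Detection in Protocol Section 12 and SAP Section 10 to match Protocol Section 9: every ICD Episode during confirmed WCD wear is annotated, whether or not a WCD Episode matches it.
2. Add a third, neutral class beside True Positive Detections and Missed Events, for example *discordant WCD/ICD annotation*. It holds pairs in which the ICD Episode is annotated as VT/VF of at least 187 bpm for at least 20 seconds and the WCD annotation does not meet the True Positive Detection definition. For each pair, state whether a Shock Alarm Event Marker was present.
3. Show the class in the Appendix A listing, and check that the Charter uses the same scope.

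The cost is wording in two documents and a small extra reading load for a committee to which Protocol Section 9 already assigns all ICD episodes. SAP Section 9 allows such a change by amendment before the primary endpoint is analysed.
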